4.6 Validity Review

The results of the validity review meetings will be documented in the validity review reports and may comprise decisions and details relevant for statistical evaluation. Any changes to the statistical analysis prompted by the results of the validity review meetings will be documented in an amendment and, if applicable, in a supplement to this SAP.

4.7 Testing procedure and multiplicity adjustment

If the decision will be to stop the study early for success (see section 4.4 for a description of the stopping rules), the final primary analyses, both for the primary and secondary efficacy endpoints, will be performed at a two-sided significance level of 0.270%. Only if both the primary and the key secondary efficacy endpoint achieve this significance level, the corresponding null hypotheses can be rejected and the remaining secondary endpoints will also be tested at a two-sided level of 0.270% according to the following hierarchy:

- Time to all-cause mortality
- Time to all-cause hospitalization
- Change in UACR from baseline to Month 4
- Time to first occurrence of the following renal composite endpoint: onset of kidney failure, a sustained decrease in eGFR of $\geq 57\%$ from baseline over at least 4 weeks or renal death.

If the decision will be not to stop the study early for success, the final primary analyses will be performed as follows: A group sequential design with a single interim analysis when 2/3 of the information is available with a stopping rule of two-sided $p < 0.00270$ requires a small adjustment to the final analysis that is slightly lower than $p = 0.05$ to maintain the overall significance level at 5%. The weighted Bonferroni-Holm procedure will be used for the hierarchical testing of the primary and secondary efficacy endpoints with the following adjusted alpha levels, which apply for an information fraction of 2/3:

- If the primary renal composite endpoint achieves statistical significance at a two-sided p value ≤ 0.03282695 , the secondary CV endpoint will be tested at the two-sided 0.04967388 level.
- Alternatively, if the secondary CV endpoint achieves statistical significance at a two-sided p value ≤ 0.01576184 , the primary renal composite endpoint will be tested at the two-sided 0.04967388 level.
- Only if both the renal and CV endpoints achieve formal statistical significance, the remaining secondary endpoints will be tested at a two-sided level of 0.04967388 according to the hierarchy above.

According to Tang and Geller (1999) [9] this procedure controls the overall familywise error rate at 5%.

If the testing strategy stops at one point due to a non-significant result, the testing of the remaining secondary efficacy variables will be performed in an explorative manner only.

5. Analysis Sets

Subjects will be excluded from all below-mentioned analysis sets if they are related to critical GCP violations.

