According to the size of this study it is justified to assume under H_0 a sufficiently close approximation of the log-rank test (48) to the normal distribution. If the z-value from the log-rank test (for the difference $S_{\text{finerenone}} - S_{\text{placebo}}$), stratified by the stratification factors (type of albuminuria, region, eGFR category) is larger than the critical quantile from the normal distribution ($z_{0.975} = 1.960$ or $z_{0.9833} = 2.128$), the null hypothesis will be rejected in favor of the alternative hypothesis.

The nominal significance levels and the critical values at the final analysis will be adjusted to account for the interim analysis, see Section 10.5 for more details.

In order to provide a point estimate of the hazard ratio and a corresponding two-sided 95% or 96.67% confidence interval, a stratified Cox proportional regression model will be used. Kaplan-Meier curves will be provided for the cumulative proportions of events by treatment groups.

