10.5 Planned interim analyses - amended

This section was changed in Amendment 3, see Section 15.1.2.42.

One formal interim analysis is planned when 2/3 of the required total number of primary efficacy endpoint events have been observed. Based on the assumptions from sample size determination the interim analysis will take place about 34 months after start of study treatment. As an event-driven trial, the actual timing of the interim analysis will depend on the observed event rate, the patient recruitment rate, and length of the recruitment period.

If the interim analysis shows clear and consistent benefit in the finerenone treatment group, the DMC may recommend early study termination. The Haybittle-Peto rule will be used to guide the decision regarding early stopping of the study for success: a reduction of 3 standard deviations in the analysis of the primary efficacy endpoint and the secondary CV composite endpoint at the interim analysis (two-sided p-value < 0.00270).

If the decision will be to stop the study early for success, the final primary analyses, both for the primary and secondary efficacy endpoints, will be performed at an overall two-sided significance level of 0.270%. A group sequential design with a single interim analysis when 2/3 of the information is available with a stopping rule of two-sided $p < 0.00270$ would require a final $p < 0.04967$ ($p < 0.03283$, $p < 0.01576$) to maintain the overall significance level at 5% (3.333%, 1.667%). Consequently, if the decision will be to continue the study without stopping early for success, the following testing procedure at the final analysis will control the overall familywise error rate at 5% according to Tang and Geller (1999) (53).

- If the primary renal composite endpoint achieves statistical significance at a two-sided p value ≤ 0.03283 ($z_{0.9836} = 2.134$), the secondary CV endpoint will be tested at the two sided level of 0.04967 ($z_{0.9752} = 1.963$)
- Alternatively, if the secondary CV endpoint achieves statistical significance at a two sided p value ≤ 0.01576 ($z_{0.9921} = 2.414$), the primary renal composite endpoint will be tested at the two-sided level of 0.04967 ($z_{0.9752} = 1.963$)
- Only if both the renal and CV endpoints achieve formal statistical significance, the remaining secondary endpoints will be tested hierarchically at a two-sided level of 0.04967 ($z_{0.9752} = 1.963$).

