4.4 Interim Analyses and Data Monitoring

One formal interim analysis is planned when 2/3 of the required total number of primary efficacy endpoint events have been observed.

If the interim analysis shows clear and consistent benefit in the finerenone treatment group, the DMC may recommend early study termination. The Haybittle-Peto rule will be used to guide the decision regarding early stopping of the study for success: a reduction of 3 standard deviations in the analysis of the primary and the key secondary efficacy endpoint at the interim analysis (two-sided p-value <0.00270).

For a detailed description of the testing procedure, including an adjustment of the significance level for the interim analysis, please see section 4.7.

In case of an early stop of the study for success, the final analysis reported in the CSR will consider all events up to the subjects' respective EoS visits as would have been the case if the study had not stopped early. A sensitivity analysis will take all events up to the interim analysis datacut date into consideration and will be based on the same final clean database as done for the final analysis reported in the CSR (instead of the interim analysis database). For this sensitivity analysis, censoring dates after the datacut date will be reset to the datacut date.

For a lack of efficacy, a non-binding futility approach will be utilized at the time of the planned interim analysis. If the conditional probability of rejecting the null hypothesis for the primary comparison, given the assumed and current event rates, falls to an unacceptably low level (as specified in the DMC Charter), the DMC may consider recommending early termination of the study.

A detailed plan for the routine DMC safety analyses and the interim analysis is covered in the DMC charter, the analysis planned to be provided to the DMC is described in a separate DMC SAP with Tables, Listings and Figures (TLFs) attached to the DMC charter. The DMC will review the data in an unblinded manner, both for the routine safety tables and the interim analysis. There are no predefined stopping conditions for the ongoing safety monitoring of this trial. The statistical analysis for the DMC meetings will be performed by an independent statistical analysis center.

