In order to provide a point estimate of the hazard ratio and a corresponding two-sided 95% confidence interval, a stratified Cox proportional hazard regression model will be used. The stratification variables will be included in the STRATA statement in SAS PROC PHREG, which will assume proportional hazards for each level of one particular stratification factor.

Kaplan Meier curves will be provided for the cumulative incidence risk of outcome events by treatment groups.

To derive the logrank test statistic and the corresponding p-value, SAS program code corresponding to the following will be used:

```
PROC LIFETEST DATA = <dataset> ALPHA=0.05 METHOD=KM;
  TIME ttevalue * ttecnsr(1);
  STRATA {stratumn} / GROUP=trtgrpnr TEST=(logrank);
RUN;

/*
where
dataset = name of sub-dataset including all ITT subjects
randomized
trtgrpnr = variable coding randomized treatment group
ttevalue = time to first occurrence of primary efficacy
outcome event
ttecnsr = censoring index (1 = right-censored, 0 = event)
stratumn = variables for stratification factors
*/
```

For the Cox proportional hazard regression SAS program code corresponding to the following will be used:

```
PROC PHREG DATA = <dataset>;
  MODEL ttevalue * ttecnsr(1) = trtgrpnr / RL TIES=EFRON
ALPHA=0.05;
  STRATA {stratumn};
RUN;
```

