- Increase the inflation factor until upper limit of two-sided confidence interval for the hazard ratio crosses 1.0; this will be the “tipping point”. The actual confidence level of the above mentioned confidence interval will depend on whether the study is stopped for overwhelming efficacy at the interim analysis or not, and on the p-value of the primary analysis of the key secondary endpoint. The confidence intervals will be as follows:
 - At the interim analysis: Use two-sided 99.73% confidence interval
 - At the final analysis:
 - p-value of primary analysis of key secondary endpoint < 0.01576184 :
Use two-sided 95.032612% confidence interval
 - p-value of primary analysis of key secondary endpoint ≥ 0.01576184 :
Use two-sided 96.717305% confidence interval

The tipping point will show how much higher the event risk after drop-out would need to be in the finerenone group so that statistical significance is lost. Since there is no particular reason to assume that the event rate should be higher, a large tipping point will indicate robustness of the study results. Technical details of the model are provided in section 9.1.

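### After an early stop, SAP 4.7 rejects neither the renal nor the CV null unless both stay below 0.0027 at the end-of-study visits, a condition absent from Protocol 10.5; the fixed 95% CI in SAP 6.2.1.1 need not match the test level

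*SAP*

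**What the plan says.** **Early stop.** Protocol 10.5 and SAP 4.4 guide stopping for success by a 3-standard-deviation result (two-sided p<0.00270) on both the renal primary and the CV key secondary endpoint at the interim. If the trial stops, Protocol 10.5 says the primary and secondary analyses "will be performed at an overall two-sided significance level of 0.270" percent. It says nothing about one endpoint blocking the other. Its requirement that both be significant belongs to the no-stop branch and controls only access to the remaining secondary endpoints. SAP 4.7 adds, for the early-stop branch: "Only if both the primary and the key secondary efficacy endpoint achieve this significance level, the corresponding null hypotheses can be rejected".

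**Data used.** SAP 4.4 says that after an early stop "the final analysis reported in the CSR will consider all events up to the" subjects' own end-of-study visits. The interim cut is kept only as a secondary check: "A sensitivity analysis will take all events up to the interim analysis datacut date into consideration".

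**Interval for the primary hazard ratio.** SAP 6.2.1.1: "In order to provide a point estimate of the hazard ratio and a corresponding two-sided 95% confidence interval", with ALPHA=0.05 in the code. Protocol 10.3.3.1 instead asks for a "point estimate of the hazard ratio and a corresponding two-sided 95% or 96.67% confidence interval". The tipping-point analysis in SAP 6.2.1.2 matches its interval to the test. After a stop: "At the interim analysis: Use two-sided 99.73% confidence interval". At the planned final analysis with CV not significant at its first step: "Use two-sided 96.717305% confidence interval". Otherwise it uses 95.032612%.

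**The concern.** The joint clause makes both endpoints clear 0.0027 a second time, on a different data set, before either null can be rejected. A trial stopped for benefit on both endpoints could therefore lose its primary claim through a small movement in CV after the interim cut, when no further data can be collected.

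The clause also sits badly with the rest of SAP 4.7. Take renal p=0.0001 and CV p=0.004. At the planned final analysis, renal passes 0.03282695, CV is then tested at 0.04967388 and passes, and both nulls are rejected. After a stop for strong benefit, the same pair rejects neither.

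The interval is a lesser matter. The decision rests on the stratified logrank test, but a reader shown a 95% interval below 1 beside a failed primary test is given two conflicting signals. The SAP avoids this in its sensitivity analysis but not in its primary one.

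**Working it through.** **1. The plan's final levels.** Inputs from Protocol 10.5 and SAP 4.7: one interim at information fraction 2/3, two-sided boundary |z|=3 (p=0.0027). With correlation √(2/3) between looks, solve P(|Z₁|>3 or |Z₂|>c)=α for c:

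| Overall α | c | Final two-sided level | SAP 4.7 |
|---|---|---|---|
| 5% | 1.963 | 0.049674 | 0.04967388 |
| 3.333% | 2.134 | 0.032827 | 0.03282695 |
| 1.667% | 2.414 | 0.015761 | 0.01576184 |

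The figures agree to at least five decimal places, so each local test has already been charged for crossing at the interim.

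**2. Does error control need the joint clause?** Suppose the trial stops when both endpoints cross and each null is then judged separately at 0.0027. Any rejection after a stop lies inside |z|>3 at the interim for that endpoint, which step 1 has paid for. With one true null, its error is at most 5%. With both true, it is at most 3.333%+1.667%=5%. Simulated familywise error under separate rejection is 0.049 (renal null only), 0.048 (both null) and 0.049 (CV null only).

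**3. What the clause costs.** Renal events at the interim: 1068×2/3=712. The documents give no CV event count, CV effect, correlation or overrun, so these are assumptions: 400 or 550 CV events at the interim; renal and CV hazard ratios each 0.75, 0.80 or 0.85; overrun 5% or 20%; correlation 0.2; a stop at every joint crossing. That makes 36 scenarios. For d events at the interim and o afterwards,

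z_interim ~ N(½√d·|ln HR|, 1), and z_EoS = (√d·z_interim + √o·z_new)/√(d+o), with z_new ~ N(½√o·|ln HR|, 1).

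The documents do allow a rough scale for overrun. Protocol 10.5 puts the interim at about month 34 and Protocol 10.4 the end at month 44, so 1068−712=356 events in 10 months, about 36 a month. A 5% overrun (36 events) is about one month and 20% (142 events) about four.

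Results from 1.5 million draws per scenario:

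| Renal HR / CV HR | CV events | Overrun | Stops | Some endpoint misses, of stops | Renal rejection lost to CV alone, of stops | Same, of all trials |
|---|---|---|---|---|---|---|
| 0.80 / 0.80 | 550 | 5% | 20% | 9% | 5% | 1.1% |
| 0.80 / 0.80 | 550 | 20% | 20% | 11% | 7% | 1.4% |
| 0.75 / 0.85 | 400 | 20% | 8% | 21% | 20% | 1.5% |
| 0.85 / 0.85 | 400 | 20% | 3% | 27% | 16% | 0.4% |
| All 36 scenarios | | | 3–54% | 4–27% | 2–20% | 0.3–2.3% |

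Correlation 0 or 0.4 gives 0.2–2.4% of all trials. If both interim z values exceed 3.5, the renal loss falls to 0.02–4% of stops, so narrow crossings drive it.

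**4. Interval against test.** With 1:1 allocation the standard error of ln HR is about 2/√D, so the critical hazard ratio is exp(−2z/√D).

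- Planned final, D=1068, level 3.283%: exp(−2×2.134/√1068)=0.878. For the 95% interval: exp(−2×1.960/√1068)=0.887. Between the two, the interval excludes 1 and the test fails.
- Example: p=0.04 gives HR 0.882, with upper limit 0.994 at 95% and 1.005 at 96.717305%.
- Chance of a mismatch, with no stop and CV p at or above 0.01576 (600–825 CV events at the end, CV HR 0.80–0.85): 0.6–2.0% at a true renal HR of 0.80–0.81, and 1.4–4.1% at 0.85. The 0.81 is the effect at which 1068 events give 90% power at 3.333% (HR 0.812).
- After a stop, exp(−6/√D) to exp(−3.92/√D): 0.803–0.866 for D=748 and 0.814–0.874 for D=854.
- At the 4.967% level, 95% and 95.03% are effectively the same.

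**The case against.** The clause can be read as deliberate. The stopping guide already requires both endpoints and speaks of clear and consistent benefit; SAP 4.7 carries that joint standard into the reported analysis. Protocol 10.1 leaves detail to the SAP, and SAP 7.2 records that the testing procedure was fully specified in the new section. Protocol 10.5 is silent on one endpoint slipping, so no protocol sentence is contradicted. Whether a trial stopped on two endpoints should be able to claim only one is partly a design preference.

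The larger percentages also come from unfavourable corners. The 27% arises where only 3% of trials stop. The 20% needs a renal effect stronger than the design value together with a weak CV effect. The four-week window for end-of-study visits points towards 5% overrun rather than 20%, and the monitoring committee, which only receives guidance, need not stop on a bare crossing.

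On the interval, no decision uses it, 95% is one of the protocol's two named levels, and the protocol's 96.67% would not match the interim-adjusted level exactly either.

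Most of this stands as to weight. The unconditional loss is small and the interval is presentation. It does not supply a reason for the clause: it buys no error control, it reverses the conclusion that SAP 4.7 would draw from the same p-values at the planned final analysis, and SAP 7.2 does not identify it as an added condition.

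**Conclusion.** The concern holds on both parts. After an early stop, SAP 4.7 withholds every rejection unless renal and CV both remain below 0.0027 on the end-of-study data. Protocol 10.5 does not ask for this and the alpha allocation does not require it. The effect is conservative: a renal rejection is lost to CV drift in about 2–20% of stops and 0.3–2.3% of all trials. Those figures rest on the assumed CV counts, effects, correlation and overrun, and on stopping at every joint crossing. For a trial stopped well beyond the boundary the risk is slight.

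The fixed 95% interval departs from Protocol 10.3.3.1 and from the SAP's own tipping-point analysis. It can disagree with the primary test at the 3.283% level and, over a wider range, after an early stop. It affects reporting, not the decision. Both are worth correcting because the correction is cheap; neither threatens the validity of a claim the trial could make.

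**What to change.** **SAP 4.7.** After an early stop, reject the renal null if its p<0.0027 and the CV null if its p<0.0027, each on its own. Proceed to the remaining secondary hierarchy only if both are rejected. If a joint claim is truly intended, say so and justify it in the protocol as well.

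**SAP 6.2.1.1.** Report the primary hazard ratio with the interval matching the level applied: 96.717305%, 95.032612% or 99.73%, as SAP 6.2.1.2 already does. A 95% interval may stand beside it, labelled as descriptive.

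**Cost.** SAP wording and one ALPHA= setting, with no familywise error cost. The matched interval is wider on the log scale by 2.134/1.960, about 9%, at 96.717305%, and by 3/1.960, about 53%, at 99.73%. An early stop could then end with a renal claim alone, which the present clause rules out; the sponsor should accept that knowingly.

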5.1 Safety analysis set (SAF)

All randomized subjects who have taken at least 1 dose of study drug (with the exception described in Section 5).

5.2 Full analysis set (FAS)

All randomized subjects (with the exception described in Section 5).

5.3 Per-protocol analysis set (PPS)

All subjects of the FAS without any of the following validity findings:

- The subject is younger than 18 years (the lower age limit may be higher if legally required in the participating country)
- Subject without type 2 diabetes mellitus
- Subject with no clinical diagnosis of DKD (no persistent high/very high albuminuria at run-in or screening visit (UACR<30mg/g (3.4 mg/mmol))).
- Subject with clinical diagnosis of DKD and persistent high albuminuria, but eGFR < 25 mL/min/1.73 m² or ≥75 mL/min/1.73 m² or missing at run-in or screening, or for patients who switched study after screening only at the screening visit
- Subject with clinical diagnosis of DKD and persistent very high albuminuria, but eGFR < 25 mL/min/1.73 m² or ≥60 mL/min/1.73 m² or missing at run-in or screening visit, or for patients who switched study after screening only at the screening visit
- Subject with clinical diagnosis of DKD and persistent high albuminuria, but no history of diabetic retinopathy in the medical history
- UACR >5000 mg/g (565 mg/mmol) or missing at the run-in visit or screening visit
- Dialysis for acute renal failure within 12 weeks prior to the run-in visit
- Subject was not treated with any ACEI or ARB starting from run-in visit
- Participation in another clinical study or treatment with another investigational product 30 days prior to randomization except for the run-in and screening of study 17530
- Known significant non-diabetic renal disease, including clinically relevant renal artery stenosis
- Investigational drug other than the study drug is used concomitantly or within 30 days from stop of study drug

- An ACE inhibitor and an ARB OR more than 1 ACE inhibitor OR more than 1 ARB were used in combination during study drug treatment for more than 30 days
- Eplerenone, spironolactone, any renin inhibitor, or potassium sparing diuretic were used during study drug treatment for more than 30 days
- Potent CYP3A4 inducers were taken for more than 30 days during study drug treatment
- Wrong study medication (incorrect treatment (placebo or verum)) was dispensed to subject
- The subject is not compliant (<80%)
- The subject is not compliant (>120%)
- Subject was randomized but never received any study medication
- Visit 1 was done on the same day as screening and/or run-in visit

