6.1 Inclusion criteria

Subjects must meet all of the following inclusion criteria to be included in the study:

1. Written informed consent signed before any study-specific procedure
2. Men or women aged 18 years and older. The lower age limit may be higher if legally required in the participating country.
3. Women of childbearing potential can only be included in the study if a pregnancy test is negative at the Screening Visit and if they agree to use adequate contraception. Adequate contraception is defined as any combination of at least 2 effective methods of birth control, of which at least one is a physical barrier (e.g. condoms with hormonal contraception or implants or combined oral contraceptives, certain intrauterine devices). Women are considered post-menopausal and not of child-bearing potential if they have had 12 months of natural (spontaneous) amenorrhea with an appropriate clinical profile (e.g. age appropriate) or 6 months of spontaneous amenorrhea with serum FSH levels > 40 mIU/mL [for US only: FSH levels > 40 mIU/mL and estradiol < 20 pg/mL] or have had surgical treatment such as bilateral tubal ligation, bilateral ovariectomy, or hysterectomy.
4. Subjects with **type 2 diabetes mellitus** as defined by the American Diabetes Association (35)
5. Subjects with a clinical diagnosis of DKD based on either of the following criteria at the Run-in and Screening Visit:
 - Persistent **high albuminuria** defined as UACR of ≥ 30 mg/g (≥ 3.4 mg/mmol) but < 300 mg/g (< 33.9 mg/mmol) in 2 out of 3 first morning void samples and eGFR ≥ 25 but < 60 mL/min/1.73 m² (CKD-EPI) (36, 37) and presence of **diabetic retinopathy** in the medical history ⁴OR
 - Persistent **very high albuminuria** defined as UACR of ≥ 300 mg/g (≥ 33.9 mg/mmol) in 2 out of 3 first morning void samples and eGFR ≥ 25 but < 75 mL/min/1.73 m² (CKD-EPI) (36, 37) ⁵

Note: One re-assessment of eGFR and UACR is allowed at the Run-in Visit and the Screening Visit. If one of the 3 UACR measurements is missing but the other 2 are valid, these values can be used to assess subject's eligibility for this study.

⁴ **Note:** The number of subjects with high albuminuria and presence of diabetic retinopathy in the medical history will be capped at approximately 10% of the total population at screening.

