7.1 Treatments to be administered

Finerenone immediate-release (IR) tablets are light orange film-coated tablets, oval (modified oblong), containing 10 mg or 20 mg finerenone (Table 7-1). Matching placebo tablets will be supplied.

Following a Screening Visit, eligible subjects will be randomized 1:1 to either finerenone or placebo, and study drug will be dispensed according to the visit schedule (see Section 9.1).

The subject will receive the following:

- Finerenone
 - 10 mg finerenone tablet once daily (OD)
(starting dose for subjects with an eGFR between 25 to < 60 mL/min/1.73m² at the Screening Visit)
 - 20 mg finerenone tablet OD
(starting dose for subjects with an eGFR ≥ 60 mL/min/1.73m² at the Screening Visit)

or

- Placebo tablet OD.

Following randomization of the subject, the IxRS will determine the bottle number for the study site investigator or designee to select for the subject. The investigator at the study site is to instruct subjects to take 1 tablet OD, preferably in the morning. The first dose of study drug should be taken at the site on the same day as Visit 1 (Day 1), preferably in the morning.

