7.3 Treatment assignment

Eligible subjects will be randomized within ≤ 2 weeks after the Screening Visit. The randomization will be stratified by region (North America, Europe, Asia, Latin America and others), type of albuminuria at screening (high or very high albuminuria) and eGFR at screening (25 to <45 , 45 to <60 , ≥ 60 mL/min/1.73m²). The eGFR will be calculated by the Central Laboratory applying the CKD-EPI formula (36).

The number of subjects with eGFR ≥ 60 to <75 mL/min/1.73 m² and very high albuminuria will be capped at approximately 10% of the total population with very high albuminuria at screening. The number of subjects with high albuminuria and presence of diabetic retinopathy in the medical history will be capped at approximately 10% of the total population at screening.

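### SAP 5.3 attaches the two eGFR upper limits to the wrong albuminuria classes, so the per-protocol set drops eligible patients with eGFR 60 to <75

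*SAP*

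**What the plan says.** Protocol 6.1, criterion 5, gives two routes into the trial:

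- High albuminuria with a history of diabetic retinopathy requires "eGFR ≥ 25 but < 60 mL/min/1.73 m² (CKD-EPI").
- Very high albuminuria requires "eGFR ≥ 25 but < 75 mL/min/1.73 m² (CKD-EPI").

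The protocol plans for the upper band of the second route. Section 3.3 explains why such patients are included. Section 7.3 says that the number with very high albuminuria and eGFR 60 to <75 "will be capped at approximately 10% of the total population with very high albuminuria at screening".

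SAP 5.3 defines the PPS as the FAS without a list of validity findings. Two of them concern eGFR by albuminuria class:

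- "persistent high albuminuria, but eGFR < 25 mL/min/1.73 m² or ≥75 mL/min/1.73 m² or missing at run-in or screening"
- "persistent very high albuminuria, but eGFR < 25 mL/min/1.73 m² or ≥60 mL/min/1.73 m² or missing at run-in or screening visit"

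A further finding removes subjects with "persistent high albuminuria, but no history of diabetic retinopathy in the medical history". It sets no eGFR limit.

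**The concern.** The limits of 60 and 75 appear in both documents but are paired with opposite albuminuria classes. A validity finding should mark a departure from the protocol. Here, meeting an inclusion criterion counts as one, and breaching the other criterion between 60 and 75 does not.

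The error falls on one stratum. Under the protocol, only patients with very high albuminuria can be eligible in the screening eGFR ≥60 stratum, one of the three eGFR levels used in randomisation. Protocol 7.1 also makes the 20 mg tablet the "starting dose for subjects with an eGFR ≥ 60 mL/min/1.73m² at the Screening Visit". The rule therefore removes all eligible patients in that stratum, on 20 mg finerenone or matching placebo.

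The PPS is used widely. It repeats the primary endpoint (SAP 6.2.1.2), the secondary endpoints including UACR at Month 4 (6.2.2.2) and the exploratory endpoints (6.2.3). Kaplan-Meier results are planned in the PPS by level of each stratification factor. Exposure by screening eGFR category, and titration status by starting dose, are repeated in the PPS when its size differs from the FAS (6.1.5). The ≥60 and 20 mg cells of these outputs would hold no eligible patients. Validity findings are also tabulated by treatment group (6.1.1), so correctly enrolled patients would be reported as having one.

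**Working it through.** The plan gives no expected PPS size, so there is no figure of its own to reproduce. The check is a comparison of rules, followed by a count based on the caps.

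**Step 1: compare the rules by eGFR band** (mL/min/1.73 m²; high albuminuria taken with retinopathy).

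| Class | eGFR | Eligible (Protocol 6.1) | Kept by SAP 5.3 | Agree |
|---|---|---|---|---|
| High | <25 | no | no | yes |
| High | 25 to <60 | yes | yes | yes |
| High | 60 to <75 | no | yes | **no** |
| High | ≥75 | no | no | yes |
| Very high | <25 | no | no | yes |
| Very high | 25 to <60 | yes | yes | yes |
| Very high | 60 to <75 | yes | no | **no** |
| Very high | ≥75 | no | no | yes |

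The rules disagree in the 60 to <75 band in both classes and nowhere else. With the two upper limits exchanged, every row agrees.

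**Step 2: look for signs of intent.** SAP 4.1 gives very high albuminuria with eGFR ≥75 as its example of a combination that does not exist in the study, so the SAP itself places that limit at 75. The change histories in SAP 7.1 to 7.3 record no decision to alter these limits. No other PPS finding restores them.

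**Step 3: size of the wrongly excluded group.** Inputs:

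- Cap on eGFR 60 to <75: about 10% of the very-high-albuminuria population (Protocol 7.3).
- Cap on high albuminuria with retinopathy: Protocol 7.3 says the number "in the medical history will be capped at approximately 10% of the total population at screening".
- Number randomised: 4800 (Protocol 10.4) or about 5800 (SAP 3).

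Wrongly excluded = 0.10 × (share with very high albuminuria) × N.

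| Share with very high albuminuria | N = 4800 | N = 5800 | Percent of N |
|---|---|---|---|
| 0.90 (both caps full) | 0.10 × 4320 = 432 | 0.10 × 5220 = 522 | 9% |
| 1.00 (no high albuminuria) | 0.10 × 4800 = 480 | 0.10 × 5800 = 580 | 10% |

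If the eGFR cap is not filled, the number falls in proportion.

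**Step 4: what the caps do not count.** The finding is triggered by either visit, except that patients who switched study after screening are judged at screening only. A patient with very high albuminuria and eGFR 60 to <75 at run-in but <60 at screening is eligible and is also removed. The documents do not give that number. The number wrongly kept depends on how many entry violations occurred and cannot be derived.

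**Step 5: precision.** If events fall in proportion to patients, a 9% loss widens the standard error of the log hazard ratio by 1/√0.91 = 1.048, about 5%.

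**The case against.** The mismatch itself is not in dispute. The case on the other side concerns how much it matters.

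- **The PPS is supportive.** The primary and secondary tests and the alpha allocation rest on the FAS. This stands: type I error and the main conclusion are untouched.
- **The exclusion should not favour an arm.** It uses pre-randomisation eGFR, and randomisation is stratified by screening eGFR, so losses should be balanced. This also stands. The rule changes the PPS population and its precision; it does not by itself bias the comparison. As an illustration on assumed values, suppose the removed group held 9% of events with a hazard ratio of 1.0 and the rest had 0.80. The pooled ratio would be about exp(0.91 × ln 0.80) = 0.816, against 0.80 without that group.
- **The stratum may not be literally empty.** Ineligible patients with high albuminuria, retinopathy and eGFR ≥60 at screening could remain in it. That is correct, but any patients left there would be entry violations. About half of those removed would be on placebo, because allocation is 1:1.
- **Practice may differ from the text.** Set membership is decided in validity review meetings, and the SAP cites a separate assessment-criteria document that may hold the right limits. Whether any patient was dropped is therefore unknown. Even so, the approved SAP is the pre-specified definition, and it is wrong as written.

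**Conclusion.** The concern holds. SAP 5.3 contradicts Protocol 6.1 across the whole eGFR 60 to <75 band in both albuminuria classes, and it is inconsistent with SAP 4.1. Followed as written, it removes every eligible patient in the screening eGFR ≥60 stratum. That is 9% of those randomised if both approximate caps fill, and up to 10% if few patients have high albuminuria, plus an unknown number removed on run-in eGFR alone. It is fewer if the eGFR cap is not reached. The number of ineligible patients kept is unknown and limited to entry violations.

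FAS inference is unaffected. What is lost is the meaning of the per-protocol analysis: agreement or disagreement with the FAS would partly reflect the mistaken removal of the highest-eGFR stratum.

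**What to change.** In SAP 5.3, exchange the two upper limits so that they match Protocol 6.1:

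- High albuminuria is a validity finding if eGFR is <25, ≥60 or missing.
- Very high albuminuria is a validity finding if eGFR is <25, ≥75 or missing.

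Check that the assessment-criteria document and the validity-finding program use the same limits, then re-run the PPS flag. If the program already follows the protocol, the SAP text still needs correcting so that the two agree.

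The cost is two numbers in the SAP and one re-run of the flag. It should be done before sets are assigned at database lock (SAP 5.6) and before unblinding (SAP 4.1), because later it would be a change to an analysis set with results in view.
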